2.8 Statistical analysis

Statistics will be performed using SPSS (IBM, Chicago, IL). The significance level will be set on 5%. Descriptive statistics will be calculated for baseline participant characteristics. Means and standard deviations will be calculated for continues variables and frequencies and percentages for categorical variables. Active participation will be measured continuously during the session. Data analysis of the average of every minute will be conducted. To investigate the effect of time, the different OF speeds, and the different VEs, repeated-measures ANOVA (within-between subject design) will be done.

3. Funding

The author disclosed receipt of the following financial support for the research, authorship and/or publication of this study: fellowship of the Vrije Universiteit Brussel for one year.

4. References

- [1] I. Schwartz and Z. Meiner, "Robotic-assisted gait training in neurological patients: who may benefit?," (in eng), *Ann Biomed Eng*, vol. 43, no. 5, pp. 1260-9, May 2015.
- [2] H. K. Kang, Y. Kim, Y. Chung, and S. Hwang, "Effects of treadmill training with optic flow on balance and gait in individuals following stroke: randomized controlled trials," *Clinical Rehabilitation*, vol. 26, no. 3, pp. 246-255, Mar 2012.
- [3] O. Stoller, M. Waser, L. Stammler, and C. Schuster, "Evaluation of robot-assisted gait training using integrated biofeedback in neurologic disorders," (in eng), *Gait Posture*, vol. 35, no. 4, pp. 595-600, Apr 2012.
- [4] E. Swinnen, D. Beckwee, D. Pinte, R. Meeusen, J. P. Baeyens, and E. Kerckhofs, "Treadmill training in multiple sclerosis: can body weight support or robot assistance provide added value? A systematic review," (in eng), *Mult Scler Int*, vol. 2012, p. 240274, 2012.
- [5] I. Schwartz *et al.*, "Robot-assisted gait training in multiple sclerosis patients: a randomized trial," (in eng), *Mult Scler*, vol. 18, no. 6, pp. 881-90, Jun 2012.
- [6] K. Y. Nam, H. J. Kim, B. S. Kwon, J. W. Park, H. J. Lee, and A. Yoo, "Robot-assisted gait training (Lokomat) improves walking function and activity in people with spinal cord injury: a systematic review," (in eng), *J Neuroeng Rehabil*, vol. 14, no. 1, p. 24, Mar 23 2017.
- [7] A. Lamontagne, J. Fung, B. J. McFadyen, and J. Faubert, "Modulation of walking speed by changing optic flow in persons with stroke," *Journal of Neuroengineering and Rehabilitation*, vol. 4, Jun 2007.

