2.7 Outcome

2.7.1 Biomechanical quantification of active participation

The active participation during RAGT will be measured with the use of electromyography, the force sensors and the position sensors of the Lokomat.

- **Electromyography:** with the use of surface electrodes, muscle activity of the Mm. rectus femoris and Mm. biceps femoris of both legs will be measured. Surface electromyograms of these muscles will be analyzed with the use of the 'mean absolute value' variable. It represents the area under the EMG signal (AUC) once it has been rectified, meaning that all of the negative voltage values have been made positive. The mean absolute value will be measured per minute to compare the amount of muscle activity in time within one OF speed, between different OF speeds and between the 2 VEs.

- **Force sensors:** with the use of the force sensors of the Lokomat, interaction torques between the participant and the orthosis will be measured of the 4 joints (bilateral hip and knee). These interaction torques will be used to quantify how much the participant contributes to the walking movement him or herself. The average of these interaction torques will be calculated per minute to compare the amount of force in time within one OF speed, between different OF speeds and between the 2 VEs.
- **Position sensors:** with the use of the position sensors of the Lokomat, it is possible to measure the range of motion (°) of the 4 joints (bilateral hip and knee).

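### No primary outcome or multiplicity rule is set for active participation, so the error rate for the optic-flow aim is uncontrolled and the stated power belongs to no named outcome

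*Combined protocol and SAP*

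**What the plan says.** Section 1.2 gives two ordered aims, the effect of OF speed and then the effect of VE, both on active participation. Section 2.7.1 defines that construct by instrument: "The active participation during RAGT will be measured with the use of electromyography, the force sensors and the position sensors of the Lokomat".

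- **EMG:** "muscle activity of the Mm. rectus femoris and Mm. biceps femoris of both legs will be measured", which makes four muscle sites. The stated purpose is to "compare the amount of muscle activity in time within one OF speed, between different OF speeds and between the 2 VEs".
- **Interaction torque:** four joints, to "compare the amount of force in time within one OF speed, between different OF speeds and between the 2 VEs". Section 2.6 adds that the Lokomat yields a swing and a stance value for each driven joint, eight per step cycle.
- **Range of motion (ROM):** four joints. Section 2.7.1 says only that "it is possible to measure the range of motion" and states no comparison, but section 2.6 says the position sensors will be used for this purpose.

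The averaging described for EMG and torque is by minute. On the test level, section 2.8 says "The significance level will be set on 5" per cent. The analysis in section 2.8 is one sentence: "To investigate the effect of time, the different OF speeds, and the different VEs, repeated-measures ANOVA (within-between subject design) will be done". It names no dependent variable, primary outcome or multiplicity rule. Section 2.2.1 sizes a single within-between F-test (f = 0.25, type 1 error 0.05, power 0.80, 28 participants) and attaches it to no outcome.

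**The concern.** The first aim is one question, but the plan can produce many answers to it, each tested at 5%, and does not say which one counts. That choice can still be made after the data are seen. A chance result in one muscle or joint could then be reported as an OF effect on active participation, in a study that section 1.1 places ahead of testing in neurological patients. For the same reason, a reader of the results could not tell which finding had the planned power.

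**Working it through.** **1. The plan's own figure.** Inputs from section 2.2.1: f = 0.25, alpha 0.05, 2 groups, 3 conditions, N = 28. Not stated, so assumed: correlation between conditions rho = 0.5, and sphericity.

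For OF or OF × VE: lambda = f² × N × 3 / (1 − rho) = 0.0625 × 28 × 3 / 0.5 = 10.5, with 2 and 52 df. Power is 0.812. At N = 26, lambda = 9.75 and power is 0.778. So 28 is reproduced, as the size for **one** such test. With two groups, the OF and OF × VE tests have the same lambda and df, hence the same power.

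**2. How many OF tests the plan allows.**
- One pooled outcome per instrument: 3.
- Separate sites: 4 EMG + 4 torque + 4 ROM = 12.
- Separate sites with swing and stance force values: 4 + 8 + 4 = 16.

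**3. Chance of at least one false OF result at 5% each.** For independent outcomes it is 1 − 0.95^K:
- K = 3: 0.143
- K = 12: 0.460
- K = 16: 0.560

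For correlated outcomes, the null OF main effect was simulated in the 2 × 3 mixed ANOVA (14 per group, F with 2 and 52 df, 20,000 runs, equal correlation r between outcomes):

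| Outcomes tested | r = 0 (exact) | r = 0.5 | r = 0.9 |
|---|---|---|---|
| 3 | 14% | 13% | 9% |
| 12 | 46% | 33% | 14% |
| 16 | 56% | 39% | 15% |

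The documents give no correlations between outcomes, so r is an assumption shown as a range. Only the OF main effect is counted; tests of time, VE and interactions would add to it.

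**4. What the remedies do** (f = 0.25, N = 28, rho = 0.5).
- One primary test at 5%: power 0.81.
- First Holm step over 11 remaining outcomes, alpha 0.05/11 = 0.0045: power about 0.48.
- First Holm step with all 12 in one family, alpha 0.05/12 = 0.0042: power about 0.47.
- A 5% primary plus a separate, ungated Holm family of 11: overall error about 7% to 9.5% by simulation. The two parts must therefore be linked.
- VE main effect at 5%: lambda = 0.0625 × 28 × 3 / (1 + 2 × 0.5) = 2.625, with 1 and 26 df. Power is about 0.34.

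**The case against.** The strongest reply is that this is a first study in healthy adults, with aims worded as investigation and no stated hypothesis, so a single confirmatory outcome is partly a matter of preference. That has weight: declaring the whole study exploratory would be legitimate. But the protocol does not do so, and it makes a formal 0.05/0.80 sample size calculation.

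A second reply is that the torque average in section 2.7.1 may already pool the joints. It may; the text says only that it is taken per minute. Even if EMG and torque were each fully pooled and ROM left untested, two unranked outcomes would remain, giving about 7–10% if either may count.

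Some stronger readings should be resisted:
- **That the false-positive rate is 46% or 56%.** These are upper ends, for independent, unpooled outcomes and a rule that any one result suffices. The plan states no such rule. A stricter one, such as two of three pooled outcomes, would give about 1–4%.
- **That no significance level is set.** It is set, at 5% per test. What is missing is control across outcomes.
- **That 28 is the wrong number.** It reproduces for one test.
- **That it matters for power whether section 2.2.1 meant OF or OF × VE.** The figures are identical.

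**Conclusion.** The concern holds as an omission in the analysis plan, and it should be corrected before analysis. If any one significant outcome may answer the first aim, the chance of a false OF claim is about 9–14% (3 outcomes), 14–46% (12) or 15–56% (16), instead of 5%. These figures rest on assumed correlations of 0.9 to 0 between outcomes, on sphericity, and on counting the OF main effect alone. The power of 0.81 rests on an assumed rho of 0.5 (0.66 at 0.3, 0.96 at 0.7) and applies to a single outcome that the plan does not identify. A reader might infer that the OF findings will be unreliable or the study too small for its first aim. The documents support neither: the outcome, pooling and decision rule are left open, and the sample fits one properly named test.

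**What to change.** **Section 2.8, before analysis.** Name one primary outcome and one primary test at 5%. One example is the OF main effect on interaction torque, of which section 2.7.1 says "These interaction torques will be used to quantify how much the participant contributes to the walking movement him or herself". Fix in advance the pooling over joints and sides, the gait phase or phases used, and the sign convention. The last matters because section 2.6 says that lower activity requires more drive force.

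**Section 2.2.1.** State that the sample size refers to that outcome and test.

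**Everything else.** Report other EMG, torque, ROM and time results as exploratory. If confirmatory claims beyond the primary are wanted, including the VE aim, list the tests in advance. Then either test them with Holm only after the primary is significant, or put the primary and the others in one Holm family.

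**Cost.** Wording only; N stays 28. The downsides should be stated openly:
- The VE aim, the reason for having two groups, and single muscle or joint findings become exploratory or face a stricter threshold.
- The planned 0.80 power applies only to the primary test, and only if that test keeps the full 5%. Power is about 0.48 at a first Holm step over 11 outcomes. In a single family of 12 the primary too would start at about 0.47.
- A VE main effect of f = 0.25 has only about 0.34 power even at 5%, so calling it confirmatory would not make it well powered.

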Appendix

Setting Lokomat
